9.1.3.3 Methylation of Relevant Genes

Both gene expression profiling and Methylation of relevant genes will be performed under the direction of [name], the co-director of breast cancer program at the Sidney Kimmel Comprehensive Cancer Center at Johns Hopkins.

Methylation of relevant genes (ERalpha, APC-1, RARbeta, cyclin D2, Twist, RASSF1A, and HIN-1) will be evaluated by Quantitative Multiplex Methylation-Specific Polymerase Chain Reaction (QM-MSP) as previously described^{39,44}. This analysis provides a quantitative assessment of methylation in each gene as well as units of cumulative methylation of the gene panel. The prediction is that methylation in specific genes will reduce as a result of treatment and will result in re-expression of the genes. Re-expression of the silenced genes will be tested by Q-R-PCR in RNA extracted from the same samples.

9.1.3.4 Tumor Histone H3 and H4 Acetylation

Analysis for tumor histone H3 and H4 acetylation will be performed at University of Maryland Pathology Department under direction of [name]. The histone acetylation will be assessed in formalin-fixed, paraffin-embedded section by immunohistochemical staining using the method that was previously described in a phase II trial of vorinostat in recurrent glioblastoma multiforme⁴⁵. However, we will use ChromaVision ACIS system for immunohistochemistry image analysis to quantify the expression of tumor histone H3 and H4 acetylation. The polyclonal antibodies that will be used are listed below:

- Acetylated histone H3, lysine 9 (1:25 dilution; Cell Signaling technology catalog# 9671L)
- Acetylated histone H4, lysine 8 (1:100 dilution; Cell Signaling technology catalog# 2594S)

9.2 Blood Samples

9.2.1 Collections

Blood samples from the following time points will be obtained in all groups of patients including both tamoxifen/anastrozole and the first/second cohort. Blood samples should be collected in the following venipuncture tubes:

1. For pharmacokinetic study (PK): One 6 ml, sodium heparin coated venipuncture tubes (BD vacutainer® green top tube).
2. For Methylation profile (MP): Two 8.5 ml, Red/Gray tiger top serum separator tubes (SST)

For patients in the pilot phase and stage 1 of the phase II portion (the initial 12 patients):

Day of Rx	Label	Time Points	Purposes
1	B0	Prior to starting treatment	PK and MP
1	B1	30 minutes after the first dose of entinostat	PK
15	B2	Day 15 (±1 day) after the first treatment BEFORE entinostat	PK
15	B3	Day 15 (±1 day) after the first treatment 30 minutes AFTER entinostat	PK
Surgery/Biopsy	B4	At the time of definitive surgery (i.e., mastectomy or lumpectomy) or the post-treatment biopsy*	MP

For patients in the stage 2 of the phase II portion (20 patients):

Day of Rx	Label	Time Points	Purposes
1	B5	Prior to starting treatment	PK and MP
15	B6	Day 15 (±1 day) after the first treatment BEFORE entinostat	PK
Surgery/Biopsy	B7	At the time of definitive surgery (i.e., mastectomy or lumpectomy) or the post-treatment biopsy*	MP

*Blood sample at the time of definitive surgery or post-treatment biopsy can be omitted if definitive surgery or post-treatment biopsy occurs within 3 days after day 15 blood collection.

9.2.2 Blood Sample Processing and Storage

All samples should be labeled with the study number, patient's study number, the date and time of collection, the cohort number (first or second), the treatment group (tamoxifen or anastrozole), and designated specimen type in section 8.2.1 (i.e. B0/B1/B2/B3). The samples should not contain patients' identifying information.

9.2.2.1 Pharmacokinetic Samples

Blood will be collected for entinostat pharmacokinetics in a sodium heparin vacutainer. Samples will be obtained at baseline on Day 1 and pre-dose Day 15. In the initial dose finding portion of the study, patients will also have 2 additional samples obtained at 0.5 hr (historical time to C_{max}) on Day 1 and Day 15. Each sample will require 5 mL of patient blood. Samples will be placed **on ice immediately** and centrifuged **within 30 minutes** of collection at 1,000 x g for 10 minutes in a refrigerated centrifuge. Plasma will be stored at -20°C until analysis. Entinostat concentrations will be determined using a validated LC/MS/MS method that will be developed by the Analytical Pharmacology Core Laboratory at the Sidney Kimmel Comprehensive Cancer Center (SKCCC) at Johns Hopkins ⁴⁶.

9.2.2.2 Methylation Profile

The samples should be processed within **two hours** of drawing the blood.

- Draw blood into two 8.5 ml SST red/grey vacutainer tubes (BD vacutainer® catalog# 367988) and invert gently 5 times to initiate clotting.
- Allow blood to clot for a minimum of 30 minutes, but not longer than 2 hours.
- Centrifuge 15-20 minutes at 3,000 rpm (1,100-2,000 x g) at room temperature or 4°C.

- Aliquot the serum (top layer) into 6 cryovials (~1 ml each aliquots). There should be approximately 3 ml of serum per vacutainer tube. All of the serum should be stored.
- Serum will be stored at -70°C or colder until batch shipment or analysis.

9.2.3 Blood Sample Submission

Instructions for the collection and shipping of samples are included below. All materials must be labeled with the study number, the patient's study number, patient initials, date of collection, the cohort number (first or second), the treatment group (tamoxifen or anastrozole), and the designated specimen type (i.e. B0, B1, or B2). The samples should not contain patients' identifying information. Please be sure to use a method of shipping that is secure and traceable. Extreme heat precautions should be taken when necessary. Shipping should be arranged only on Monday-Wednesday by overnight service to assure receipt. **Do not ship specimens on Thursday, Friday, Saturday, or Sunday** (specimens drawn on Friday should be sent the following Monday). Please notify the contact person listed below for each type of specimens via email and/or telephone **PRIOR** to shipping.

A copy of the tissue tracking form and/or the blood and serum tracking form should be included in the shipping package. Please note that if multiple samples are sent, only one copy of the form needs to be included.

9.2.3.1 Pharmacokinetic Samples

All specimens should be properly labeled as described above. **NOTE:** In the event that baseline specimens are available but the patient is not successfully registered to the protocol, do not submit the patient's specimens. Blood samples for pharmacokinetic study should be processed and stored until batch shipment at the end of the study. Samples should be shipped on dry ice and overnight shipments should occur on **Monday through Wednesday** except when the following day is a holiday. A fax or call should be placed to the Analytical Pharmacology Core Laboratory prior to shipment providing the shipment tracking information.

Address shipments and any question regarding specimen processing to:

Analytical Pharmacology Core Laboratory
 Attn: Entinostat/Anastrozole Study Samples
 [name]
 [name]
 [contact]
 Phone with voicemail: [contact]
 [contact]

9.2.3.2 Methylation Profile

All specimens should be properly labeled as described above. Blood samples for Methylation profile should be processed and stored until batch shipment at the end of the study. Samples should be shipped in dry ice overnight on **Monday through Wednesday** except when the following day is a holiday. Please contact [name] prior to the shipment and the shipment tracking information should be provided.

Address shipments and any question regarding specimen processing to:

[name].
 Sidney Kimmel Comprehensive Cancer Center at Johns Hopkins
 [name]
 [contact]
 [contact]
 Email: [contact]

9.2.4 Methods

9.2.4.1 Pharmacokinetic Study

Pharmacokinetic analysis will be performed by [name], Ph.D. at the Analytical Pharmacology Core Laboratory at SKCCC at Johns Hopkins. Patients in the pilot phase as well as stage 1 of the phase II

component of the study will have plasma samples collected four times to assess entinostat pharmacokinetics. Steady state trough concentrations ($C_{ss,min}$) will be the pretreatment concentration on Day 15. These pharmacokinetic parameters will be used to explore the relationship between entinostat exposure with pharmacodynamic (PD) endpoints such toxicity and histone acetylation in the tumors. Levels of entinostat will be determined using a validated LC/MS/MS method by [name] at the Analytical Pharmacology Core Laboratory at Johns Hopkins⁴⁶. The pharmacokinetic schedule has been summarized below.

For patients in the pilot phase and stage 1 of the phase II portion (the initial 12 patients):

1.	Day 1	Pretreatment	B0
2.	Day 1	0.5 hour after entinostat (Cmax)	B1
3.	Day 15	Pretreatment ($C_{ss,min}$)	B2
4.	Day 15	0.5 hour after entinostat (Cmax)	B3

For patients in the stage 2 of the phase II portion (20 patients):

1.	Day 1	Pretreatment	B5
2.	Day 15	Pretreatment ($C_{ss,min}$)	B6

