2.4 Entinostat Clinical Experience

Entinostat is a histone deacetylase (HDAC) inhibitor that selectively inhibits HDACs 1, 2, and 3. By promoting hyperacetylation of nucleosomal histones, entinostat promotes transcriptional activation of certain set of genes which leads to inhibition of cell proliferation, induction of terminal differentiation, and apoptosis. Multiple studies both *in vitro* and *in vivo* demonstrated that entinostat can inhibit growth of multiple tumors including breast, lung, prostate pancreatic, renal cell, and glioblastoma^{10,11}. Due to the selectivity of entinostat towards HDACs 1, 2, and 3, entinostat has a distinct safety and efficacy profiles compared to pan-HDAC inhibitors like vorinostat. Early clinical studies showed that entinostat has a remarkably long half-life which allows weekly or biweekly treatment dosing¹². In phase I pharmacokinetic study, entinostat has a half-life ranging from 40 hours to 120 hours. The level of entinostat was still detectable at 168 hours after the dose of 6 mg/m² to 12 mg/m². Pharmacodynamic studies confirm an inhibition of HDAC by entinostat in phase I study participants at all dose levels (ranging between 2 and 12 mg/m² and from once daily to every 2 weeks) tested to date by demonstrating increase in the histone hyperacetylation. Anti-cancer activity of entinostat has been observed in wide range of advanced solid tumors and hematologic malignancies across all range of tested doses. For single agent, the MTD for solid malignancies is 4 mg/m² weekly 3 weeks on 1 week off, or

10 mg/m² every other week. In hematologic malignancies, the MTD is 6 mg/m² weekly 3 weeks on 1 week off. However, further analysis based on the body surface area and drug clearance showed that the fixed dosing is considered to be as accurate as dosing based on body surface area¹³. Entinostat is currently in phase 2 clinical development in multiple solid tumors and hematologic malignancies.

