6.1.1 Non-Hematologic Toxicities of Entinostat

The following rules will be followed for the management of adverse events that are definitely or probably due to entinostat alone. Grades are according to the active version of NCI CTCAE as per section 7.3.

Toxicity	Hold dose	Treatment	Recovery	Dose reduction
Grade ≥ 3	Until recovery to grade 1 or baseline	Symptomatic remedies, start prophylaxis	If recovered by next scheduled dose	Resume at one dose level below the current dose
			If not recovered by next scheduled dose	Skip this dosing; resume at one dose level below the current dose after recovery
Recurrent Grade ≥ 3 despite dose reduction	Until recovery to grade 1 or baseline	Symptomatic remedies, start prophylaxis	If recovered by next scheduled dose	Resume at one dose level below the current dose
			If not recovered by next scheduled dose	Skip this dosing; resume at one dose level below the current dose every other week after recovery
Grade ≤ 2	Until recovery to grade 1 or baseline	Symptomatic remedies, start prophylaxis	If recovered by next scheduled dose	Resume at the current dose level
			If not recovered by next scheduled dose	Skip this dosing; resume at the current dose after recovery

The dose modification schemas are as follow for both postmenopausal and premenopausal women:

Dose Modification Schema for Postmenopausal Women		
Dose Level	Dose	
	Entinostat (mg)	Anastrozole (mg) daily
-1	3 mg weekly (on day 1, 8, 15, 22, and 29)	1
1	5 mg weekly (on day 1, 8, 15, 22, and 29)	1

or

Dose Modification Schema for Premenopausal Women		
Dose Level	Dose	
	Entinostat (mg)	Tamoxifen (mg) daily
-1	3 mg weekly (on day 1, 8, 15, 22, and 29)	20
1	5 mg weekly (on day 1, 8, 15, 22, and 29)	20

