10. STUDY CALENDAR AND VISIT SCHEDULE

Baseline evaluations are to be conducted within 3 weeks prior to start of protocol therapy.

For the first cohort:

Procedure	Pre-study	Week 1		Week 2		Week 3		Week 4		Week 5		Surgery ^a	Off treatment
		D1	D4-7	D8	D9-14	D15	D16-21	D22	D23-28	D29	D30-32		
Minimum treatment						Optional							
Treatment:													
Entinostat		A		A		A		A		A			
Anastrozole/Tamoxifen			B	B	B	B	B	B	B	B	B		
Clinical assessment:													
Informed consent	X												
Demographics	X												
Medical history	X												
Current medications	X	X		X		X		X		X		X	X
Physical exam	X	X		X		X		X		X		X	X
Vital signs	X	X		X		X		X		X		X	X
Height	X												
Weight	X	X		X		X		X		X		X	X
Performance status	X	X		X		X		X		X		X	X
Adverse event evaluation		X		X		X		X		X		X	X
Tumor measurement ^b	X	X		X		X		X		X		X	
Laboratory test:													
CBC w/diff, plts	X	X		X		X		X		X		X	X
Chemistries ^c	X	X		X		X		X		X		X	X
PT/INR, PTT	X											X	
Electrocardiogram	X												
Pregnancy test ^g	X												
Correlative studies (Research procedures):													
Pharmacokinetic study													
• Pilot phase, stage 1		X ^d				X ^d							
• Stage 2		X ^e				X ^e							
Methylation profile		X ^f										X ^f	
Tumor sample	X											X	

A: Entinostat: as per appropriate dose level PO weekly on day 1, 8, 15, 22 and 29 ± 2 days. Preferably 22 days.

B: Anastrozole for postmenopausal women: 1 mg PO daily starts on day 4 and continue until the day of definitive surgery (lumpectomy or mastectomy).

Tamoxifen for premenopausal women: 20 mg po daily starts on day 4 and continue until the day of definitive surgery (lumpectomy or mastectomy).

a: Within 6 days (preferably within 3 days) after the last dose of entinostat.

b: Tumor measurement: clinical tumor size, character, mobility, and location of the breast mass.

c: Chemistries: sodium, potassium, chloride, bicarbonate, BUN, creatinine, glucose, total bilirubin, calcium, total protein, albumin, AST (SGOT), ALT (SGPT), alkaline phosphatase, LDH, uric acid, phosphorus, and magnesium

d: Day 1: Prior to starting treatment
30 minutes after the first dose of entinostat

Day 15 (±1 day): BEFORE entinostat
30 minutes AFTER entinostat

e: Day 1: Prior to starting treatment

Day 15 (±1 day): BEFORE entinostat

f: Day 1: Prior to starting treatment

The day of definitive surgery (lumpectomy or mastectomy)

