- Laboratory studies: CBC with diff; chemistries including sodium, potassium, chloride, bicarbonate, BUN, creatinine, glucose, total bilirubin, calcium, total protein, albumin, AST (SGOT), ALT (SGPT) , alkaline phosphatase, LDH, uric acid, phosphorus, and magnesium
- Study Drug Administration, and Drug Accountability
- Pharmacokinetic study:
 - Pilot phase and stage 1 patients
 - Prior to the day 15 dose of entinostat
 - 30 minutes after the day 15 dose of entinostat
 - Stage 2 patients
 - Prior to the day 15 dose of entinostat
- Administration of entinostat as per appropriate dose level orally

Day 8, 22, and 29 after the first dose of entinostat

- Assessment of Concomitant Treatments including medication use
- Physical examination including examination of major body systems, height, body weight, ECOG performance status, and vital signs (temperature, blood pressure, heart rate, respiratory rate)
- Clinical tumor assessment by a breast examination including clinical tumor size, character, mobility, and location of the breast mass.
- Laboratory studies: CBC with diff; chemistries including sodium, potassium, chloride, bicarbonate, BUN, creatinine, glucose, total bilirubin, calcium, total protein, albumin, AST (SGOT), ALT (SGPT) , alkaline phosphatase, LDH, uric acid, phosphorus, and magnesium
- Study Drug Administration, and Drug Accountability
- Administration of entinostat as per appropriate dose level orally

For the first cohort:

Surgery day

The definitive surgery (i.e. lumpectomy or mastectomy) should be performed within 6 days (preferably within 3 days) after the last dose of entinostat.

- Assessment of Concomitant Treatments including medication use
- Physical examination including examination of major body systems, height, body weight, ECOG performance status, and vital signs (temperature, blood pressure, heart rate, respiratory rate)

- Clinical tumor assessment by a breast examination including clinical tumor size, character, mobility, and location of the breast mass.
- Laboratory studies: CBC with diff; chemistries including sodium, potassium, chloride, bicarbonate, BUN, creatinine, glucose, total bilirubin, calcium, total protein, albumin, AST (SGOT), ALT (SGPT) , alkaline phosphatase, LDH, uric acid, phosphorus, and magnesium
- Coagulation study: PT with INR and PTT
- Collection of tumor sample: Paraffin blocks and/or unstained slides
- Methylation profile study

For the second cohort:

The post-treatment biopsy (biopsy#2) day

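### In the first cohort the ±2 day dose window and the ±1 day PK window do not fit together, so the Day 15 trough can be drawn 96 to 240 h after the second dose and the analysis ignores the difference

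*Combined protocol and SAP*

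**What the plan says.** Four parts of the combined protocol and SAP bear on this.

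- **Definition.** Section 9.2.4.1: the steady-state trough "will be the pretreatment concentration on Day 15". This is sample B2 in the pilot phase and stage 1, and B6 in stage 2.
- **Sampling window.** Section 9.2.1 places these samples at "Day 15 (±1 day) after the first treatment", before the dose. Notes d and e of both calendars in Section 10 agree: "Day 15 (±1 day): BEFORE entinostat". Section 10.3 also requires collection "Prior to the day 15 dose of entinostat". B3 follows 30 minutes after that dose.
- **Dose window.** Note A of the first-cohort calendar gives entinostat "weekly on day 1, 8, 15, 22 and 29 ± 2 days". The second-cohort note A says only that dosing is weekly; its ±2 days is a visit window (Sections 10 and 10.3).
- **Half-life and skipped doses.** Section 2.4: "entinostat has a half-life ranging from 40 hours to 120 hours". Section 6.1.1 provides, after unresolved grade 3 or higher toxicity: "Skip this dosing; resume at one dose level below the current dose after recovery".

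Objective 3 of Section 1.3 correlates trough concentrations with histone acetylation and with the change in Ki67 and ER. Section 12.5.3 takes plasma concentrations as the exposure parameter. It does not mention elapsed time since the last dose, and no other section sets a limit on it.

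**The concern.** A trough is comparable between patients only if it is drawn at about the same time after the previous dose. Here the dose may move further than the sample, in either direction, and nothing in the analysis recovers the interval. A patient sampled late looks under-exposed and one sampled early looks over-exposed.

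The windows also clash: a site can keep every dose within its window and still be unable to draw a sample that meets the PK instructions.

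What is at stake is the exposure variable of one exploratory objective. For the 20 stage 2 patients, B6 is the only PK sample after baseline, so no other measurement can compensate.

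**Working it through.** The plan states no dose-to-sample interval, so there is no figure to reproduce.

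**Inputs.** Day 1 is the day of the first dose (10.3). With ±2 days, dose 2 falls on Day 6 to 10 and dose 3 on Day 13 to 17 (10, first-cohort note A). The PK sample falls on Day 14 to 16 (9.2.1). Half-life t is 40 to 120 h (2.4).

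**Step 1: interval since dose 2, in whole days.**
- Nominal: (15 − 8) × 24 = 168 h
- Shortest: (14 − 10) × 24 = 96 h
- Longest: (16 − 6) × 24 = 240 h

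**Step 2: can the samples be drawn in the window?**

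| Dose 3 on | In-window days not later than the dose | In-window B3 possible? |
|---|---|---|
| Day 13 | none; Days 14 to 16 are 24 to 72 h after the dose | no |
| Day 14 | 14 | yes |
| Day 15 | 14, 15 | yes |
| Day 16 | 14, 15, 16 | yes |
| Day 17 | 14, 15, 16 | no |

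**Step 3: effect on the concentration.** Assume one-compartment decay and equal doses. With s and d the hours from dose 1 to the sample and to dose 2, the concentration is proportional to C = 2^(−(s−d)/t) + 2^(−s/t).

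| | t = 40 h | t = 120 h |
|---|---|---|
| Nominal (s = 336, d = 168) | 0.0544 + 0.0030 = 0.0574 | 0.3789 + 0.1436 = 0.5225 |
| 240 h (s = 360, d = 120) | 0.0156 + 0.0020 = 0.0176 | 0.2500 + 0.1250 = 0.3750 |
| 96 h (s = 312, d = 216) | 0.1895 + 0.0045 = 0.1940 | 0.5743 + 0.1649 = 0.7393 |
| Range relative to nominal | 0.31 to 3.38 | 0.72 to 1.41 |
| Spread | 11.0-fold | 2.0-fold |

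**Step 4: related cases.**
- Day 8 dose skipped: 2^(−336/t) / C(nominal) = 0.0030/0.0574 = 5% at 40 h and 0.1436/0.5225 = 27% at 120 h.
- Day 14 sample after a Day 13 dose, with dose 2 on Day 8: [2^(−24/t) + 2^(−144/t) + 2^(−312/t)] / C(nominal) = 13.0 at 40 h and 2.8 at 120 h.
- On-schedule value after two doses as a share of true steady state: 1 − 2^(−336/t) = 99.7% at 40 h and 85.6% at 120 h. Having had only two doses is therefore the smaller problem.

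**Step 5: effect on a correlation.** In a simulation, dose 2 was uniform over ±48 h and the sample uniform over ±24 h, with log-normal variation between patients (assumed CV 30 to 50%; the documents give none). The factor by which an exposure correlation shrinks is the correlation between the log observed and the log nominal trough.

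| Half-life assumption | Shrinkage factor |
|---|---|
| All patients 40 h | 0.50 to 0.68 |
| All patients 120 h | 0.90 to 0.96 |
| Varies uniformly over 40 to 120 h, added CV 0 to 50% | 0.91 to 0.94 |

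**The case against.** The strongest reply has five parts.

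1. **The sample is already a pre-dose sample.** A reader might infer that the plan defines the trough by calendar day alone and so allows a sample after the dose. The documents do not support that: every sampling passage requires collection before entinostat. A post-dose B2 or B6 is a deviation, forced only by a third dose on Day 13. One can also argue that B2 and B3 bracket the dose within Day 15 ±1, so that the third dose is implicitly held to Day 14 to 16. That is a fair reading, but note A says otherwise and nothing states which window governs. It also leaves the 96 to 240 h range untouched, because that range comes from the second dose.
2. **The ±2 day dose window is explicit only for the first cohort.** This stands. Extending it to the second cohort is an inference from the visit window.
3. **Patients differ anyway.** This largely stands. From the stated half-lives alone, the nominal value differs 0.5225/0.0574 = 9.1-fold between a 120 h and a 40 h patient, so timing need not dominate. Uniform timing over the full windows is also pessimistic for a weekly schedule.
4. **A skipped dose is real low exposure, not a timing artefact.** This stands. Only the steady-state label is wrong.
5. **Times are recorded and the objective is exploratory.** The diary (Appendix C) has the date and time of each dose, and 9.2.2 asks for collection time on the label. But 9.2.3 lists only the date, the plan never says the times will be used, and recorded times cannot restore a sample that the windows ruled out.

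**Conclusion.** The point holds for the first cohort. In-window dosing permits 96 to 240 h since the second dose against a nominal 168 h, and the two windows conflict at Day 13 and Day 17. These follow from the text by counting days. The size in concentration, 11.0-fold at 40 h and 2.0-fold at 120 h between the extremes, rests on one-compartment decay and equal doses.

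The consequence for the analysis is modest on the most natural assumption: correlations at about 0.91 to 0.94 of their true value when half-life varies over the stated range. A reader might infer that timing can halve the correlations. That needs every patient at the shortest half-life together with an assumed CV of 30%, and the documents support neither. A reader might also quote 2^(144/t), which is 12.1-fold and 2.3-fold; that leaves out what remains of the first dose.

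The objective is exploratory. The primary endpoint and the Simon design do not depend on it. The change is worth making because it is nearly free and removes a real contradiction.

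**What to change.** 1. **Sections 9.2.1, 9.2.4.1, 10 (notes d and e) and 10.3.** Reconcile the two windows by tying the samples to the dose: B2 and B6 immediately before, and B3 30 minutes after, the third scheduled entinostat dose, on whatever day it falls within the dosing window.
2. **Section 12.5.3.** Step 1 makes the samples collectable but does not narrow the interval, which becomes (13 − 10) × 24 = 72 h to (17 − 6) × 24 = 264 h. So report the actual time since the previous dose from the recorded dose and draw times, and account for it, for example as a covariate in the planned logistic regression. Add a sensitivity analysis restricted to samples near 168 h, with the limit fixed in advance; this also serves the Mann-Whitney test, which takes no covariate. Rescaling everyone with one fixed half-life would ignore the differences in elimination that a trough should reflect.
3. **Labelling.** Do not call a post-dose sample, or one after a skipped dose, a steady-state trough. Skipped-dose patients can stay in the exposure analysis as low exposure.
4. **Section 9.2.3.** Require the collection time on the label, as 9.2.2 already does.

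The cost is wording in these sections, slightly more analysis work, and a few samples outside the sensitivity analysis. There are no new visits or blood draws, and no dosing rule changes.
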